## 1. Protocol Summary (Synopsis)

This project evaluated whether a structured discharge education session using the teach-back method improved heart failure self-care behaviors and reduced 30-day heart failure-related readmissions among hospitalized adults with systolic heart failure.

### 1.1 Objectives

- Primary Objective: To evaluate change in heart failure self-care behaviors from pre-intervention to immediate post-intervention using the European Heart Failure Self-care Behavior Scale-9 (EHFScB-9).
- Secondary Objective: To describe the 30-day heart failure-related readmission rate following the discharge teach-back intervention.
- Exploratory Objective: To explore whether the magnitude of EHFScB-9 improvement differed by readmission status (event-limited).

### 1.2 Endpoints

- Primary Endpoint: Mean change in total EHFScB-9 score (post minus pre).
- Secondary Endpoint: Proportion of participants with heart failure-related readmission within 30 days of discharge.
- Process Measures: Participation rate; completion rates for pre- and post-surveys.

### 1.3 Study Design (as implemented)

- Design: Single-site quasi-experimental pre-test/post-test quality improvement project.
- Participants: Hospitalized adults with systolic heart failure (LVEF  $\leq 40\%$ ), NYHA class II–IV, ACC/AHA stage C or D.
- Intervention: Standardized ~30-minute in-person discharge teach-back education session.
- Assessments: EHFScB-9 survey pre-intervention and immediately post-intervention; 30-day readmission review via EHR.

## 2. Background and Rationale

Heart failure is associated with high hospitalization and readmission rates. Inadequate understanding of discharge instructions and suboptimal self-management contribute to preventable rehospitalization. Teach-back is an evidence-based communication method that verifies understanding by asking patients to restate key information in their own words. This project implemented a structured teach-back discharge education workflow to improve self-care behaviors and reduce early readmissions.

## 3. Study Setting

The project was conducted on inpatient units at a single hospital site. Participant procedures occurred during routine discharge preparation; follow-up was completed via EHR review at 30 days.

## 4. Participant Eligibility

### 4.1 Inclusion Criteria

- Age  $\geq 18$  years.
- Diagnosed with systolic heart failure with left ventricular ejection fraction (LVEF)  $\leq 40\%$ .
- NYHA functional class II, III, or IV; ACC/AHA stage C or D.
- Hospitalized at the study site and clinically appropriate for discharge.
- Able to read/understand English at approximately 8th-grade level.
- Had access to a smartphone or tablet capable of scanning a QR code to complete surveys (REDCap).
- Provided electronic informed consent.

### 4.2 Exclusion Criteria

- Cognitive impairment preventing informed consent or teach-back participation.
- Non-English speaking (for this implementation).
- Declined participation.

## 5. Recruitment and Enrollment (Completed)

Potentially eligible participants were identified during hospitalization by the advanced heart failure cardiologist during routine clinical care and referred to the primary investigator for screening. The primary investigator confirmed eligibility, explained the project, emphasized voluntariness, and provided access to electronic consent and surveys via QR code.

## 6. Intervention (Completed)

### 6.1 Teach-Back Discharge Education Session

A standardized, approximately 30-minute discharge education session was delivered in the participant's hospital room by the primary investigator using teach-back. Core topics included daily weights, symptom monitoring (dyspnea, edema, fatigue), response to weight gain, fluid restriction, low-sodium diet, medication adherence, and physical activity. Participants were asked to explain key points back in their own words to confirm understanding and correct misconceptions.

### 6.2 Educational Materials

- American Heart Association: "How Can I Live with Heart Failure?"
- American Heart Association: Heart Failure Symptom Tracker.

## 7. Study Procedures and Schedule (Completed)

### 7.1 Baseline (Pre-Intervention)

- Electronic consent in REDCap via QR code.

- Creation of a participant alias to link surveys without identifying information.
- Baseline EHFSdB-9 survey (self-administered privately).

## 7.2 Intervention

- In-person teach-back discharge education (~30 minutes).
- Review and provision of printed educational materials.

## 7.3 Immediate Post-Intervention

- Post-intervention EHFSdB-9 survey in REDCap via a second QR code (self-administered privately).

## 7.4 30-Day Follow-Up

- Retrospective EHR review at 30 days post-discharge to determine heart failure-related readmission (yes/no), date, and reason.

# 8. Outcomes and Measures

## 8.1 EHFSdB-9

The European Heart Failure Self-care Behavior Scale-9 (EHFSdB-9) is a 9-item questionnaire assessing key self-care behaviors. Items are rated on a 5-point scale; lower scores indicate better self-care. The total score is the sum of items (range 9–45).

## 8.2 30-Day Heart Failure-Related Readmission

Readmission was defined as an unplanned inpatient admission for heart failure-related reasons to the study-site hospital within 30 days of index discharge and was determined through EHR review.

# 9. Enrollment and Sample Size (Actual)

A total of 57 participants were enrolled and completed both the pre- and post-intervention EHFSdB-9 surveys. Enrollment occurred during a 30-day implementation window at the single hospital site.

Key dates (Actual): Study Start Date September 11, 2025 (Actual); Primary Completion Date October 11, 2025 (Actual); Study Completion Date November 10, 2025 (Actual).

# 10. Data Collection, Management, and Confidentiality

- Survey data were collected in REDCap using de-identified aliases.
- A separate secure crosswalk list (medical record numbers only) was maintained solely for 30-day readmission ascertainment and stored in a locked location.
- Electronic files were stored on encrypted/password-protected devices per institutional policies.

- Only minimum necessary information was collected for EHR review.

#### 11. Ethical Considerations

The project was conducted with IRB approval. Participation was voluntary, and electronic informed consent was obtained prior to survey completion.

#### 12. Risks, Burden, and Benefits

- Risks were minimal and primarily related to time burden and potential fatigue during education.
- Potential benefits included improved understanding of discharge instructions and better self-care behaviors.
- Privacy was protected through de-identification and secure data handling.

#### 13. Quality Assurance

- A standardized education script and teach-back prompts were used to support fidelity.
- REDCap validation rules supported data quality.
- Completeness of surveys and follow-up ascertainment were monitored throughout the project.

#### 14. References and Supporting Documents

Copies of the EHFS cB-9 instrument and AHA education handouts were retained in secure project files in accordance with IRB and site policy.

### Key Study Dates (Actual)

Study Start Date: September 11, 2025 (Actual)

Primary Completion Date: October 11, 2025 (Actual)

Study Completion Date: November 10, 2025 (Actual)

Impact of Discharge Teach-Back Education on Heart Failure Patients' Knowledge/Self-Care

Behaviors and 30-Day Readmissions

Statistical Analysis Plan (SAP)

NCT07280208

August 14, 2025

1. Introduction

This Statistical Analysis Plan (SAP) reflects the analyses that were performed for the completed project evaluating the impact of a structured discharge teach-back education intervention on heart failure self-care behaviors and 30-day heart failure-related readmissions.

2. Key Study Dates (Actual)

- Study Start Date: September 11, 2025 (Actual)
- Primary Completion Date: October 11, 2025 (Actual)
- Study Completion Date: November 10, 2025 (Actual)

3. Study Overview (as implemented)

- Design: Single-site quasi-experimental pre-test/post-test (within-subject).
- Intervention: Approximately 30-minute discharge teach-back education session.
- Measure: European Heart Failure Self-care Behavior Scale-9 (EHFScB-9).
- Follow-up: 30-day heart failure-related readmission determined via study-site electronic health record (EHR) review.
- Actual sample: N = 57 participants with complete pre- and post-intervention EHFScB-9 assessments.

4. Demographic Reporting

Due to the relatively small sample size and the potential risk of breach of confidentiality, detailed demographic data were not reported. However, all participants met the inclusion criteria and represented a clinically appropriate population for the intervention supporting the project's aim to improve transitional care and reduce readmissions.

5. Statistical Software and Significance Threshold

- Software: IBM SPSS Statistics, Version 29.0.1.0 (171).
- Statistical significance threshold: two-sided $p < 0.05$.

6. Outcomes and Scoring

6.1 EHFScB-9 Outcomes

The EHFScB-9 includes nine self-care domains/items. Pre- and post-intervention item scores were summarized. For between-group analyses, EHFScB-9 improvement was operationalized as the pre-to-post change (improvement) score.

6.2 Readmission Outcome

Thirty-day heart failure-related readmission was coded as yes/no based on study-site EHR review.

7. Analytic Methods (Performed)

- Descriptive statistics summarized pre- and post-intervention EHFSB-9 scores.
- Paired-samples t-tests evaluated pre- to post-intervention changes across all nine EHFSB-9 domains/items.
- Because the number of readmissions was extremely low ($n = 1$), logistic regression was not feasible.
- A Mann–Whitney U test was used to compare EHFSB-9 improvement scores between the readmitted and non-readmitted groups (exploratory; underpowered).
- Scale reliability was assessed using Cronbach’s alpha (pre- and post-intervention).
- Effect sizes were calculated for the overall pre/post change using Cohen’s d and Hedges’ g .

8. Results Summary (Completed Study)

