8.2 Paired t-test Findings

Paired-samples t-tests confirmed statistically significant improvement in all nine self-care behaviors, with p -values $< .001$. The overall mean difference between pre- and post-intervention scores was 1.99, with a t -value of 16.542.

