8.6 Descriptive Improvement Scores (Non-readmitted Group)

For the non-readmitted group, the mean improvement score was -18.52 (SD = 7.26), with a median of -20.00 and a range of 30.00.

9. Limitations Relevant to Analysis

- Between-group comparisons by readmission status were underpowered due to a single readmission event ($n = 1$).
- Logistic regression modeling was not feasible because of sparse events.
- Readmissions were determined via study-site EHR review; readmissions to outside facilities may not have been captured.

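### The primary endpoint, mean change in total EHFScB-9 score, has no reported estimate, SD or 95% CI for all 57 participants, and the SAP figures that stand nearest to it do not reconcile.

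*SAP*

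**What the plan says.** Protocol 1.2 names one primary endpoint: "Primary Endpoint: Mean change in total EHFScB-9 score (post minus pre"). Protocol 8.1 fixes the scale, "The total score is the sum of items (range 9–45"), and the direction: "Items are rated on a 5-point scale; lower scores indicate better self-care". An improvement is therefore a negative number.

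SAP 6.1 summarises item scores and does not define the total as an outcome. SAP 7 states: "Paired-samples t-tests evaluated pre- to post-intervention changes across all nine EHFSB-9 domains/items". It also plans Cohen's d and Hedges' g for an overall pre/post change, without saying on which scale. The analysis set in SAP 3 is "N = 57 participants with complete pre- and post-intervention EHFScB-9 assessments".

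The results then give two figures:

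- SAP 8.2: "The overall mean difference between pre- and post-intervention scores was 1.99", with t = 16.542. Section 8.3 adds d = 2.19 and g = 2.16. No scale is named.
- SAP 8.6: "For the non-readmitted group, the mean improvement score was -18.52", with SD 7.26, median −20.00 and range 30.00. This is in 56 of the 57 participants.

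No confidence interval is printed for either.

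**The concern.** The one figure that covers everyone (1.99) is not in the endpoint's units and has the reverse of its sign. The one figure in the right units and sign (−18.52) leaves out a participant because of a later outcome. Neither is the declared endpoint. The primary objective therefore lacks its own estimate and interval.

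This would be a labelling matter if one figure could be converted into the other. They cannot be reconciled, so at least one of the reported mean difference, t, effect size, Mann–Whitney result or improvement summary does not describe the total-score change as the protocol defines it.

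**Working it through.** **Inputs.** From the SAP: n = 57 (section 3); largest item differences 2.86, 2.63 and 2.37 (8.1); all nine items improved, overall difference 1.99, t = 16.542 (8.2); d = 2.19, g = 2.16 (8.3); 56 not readmitted, 1 readmitted, U = 5.500, W = 1601.500 (8.5); mean −18.52, SD 7.26, range 30.00 (8.6). From the protocol: nine items, total 9–45, lower is better, post minus pre.

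**1. Reproduce the SAP's effect sizes.** d = t/√n = 16.542/√57 = 2.191. g = d × (1 − 3/(4 × 56 − 1)) = 2.162. Both match 8.3, so 8.2 reports one participant-level paired test on 57 people.

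**2. What scale is 1.99 on?** The three largest item differences sum to 2.86 + 2.63 + 2.37 = 7.86. Since all nine items improved, a total-score change must exceed 7.86 in size, so 1.99 is not one. As a nine-item average it implies a sum of 9 × 1.99 = 17.91, leaving (17.91 − 7.86)/6 = 1.675 on average for the other six items. That is below the third-largest difference of 2.37, so the reading is feasible. A positive value for an improvement means pre minus post.

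**3. Convert to the protocol's endpoint.** −9 × 1.99 = −17.91 (rounding range −17.96 to −17.87). The implied SD is 9 × 1.99/2.191 = 8.17.

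**4. What must the readmitted participant's change be?** 57 × (−17.91) − 56 × (−18.52) = +16.25. Allowing for rounding in both means, it lies between +13.4 and +19.1.

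**5. What do 8.5 and 8.6 allow?** W − 56 × 57/2 = 1601.5 − 1596 = 5.5 = U, so W is the rank sum of the 56. The readmitted participant's rank is 57 × 58/2 − 1601.5 = 51.5. A half rank means a tie, so at least six of the 56 lie at or above that participant's change.

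- *From the range alone:* the tied value lies within the 56's range, and their minimum cannot exceed their mean. The change is at most −18.52 + 30 = +11.48, already below +13.4.
- *From the mean and SD:* if six of the 56 lie at least c above the mean, the sum of squares is at least 6c² + (6c)²/50 = 6.72c². It cannot exceed 55 × 7.265² = 2902.9 (upper rounding limit of the SD). So c ≤ √(2902.9/6.72) = 20.78, and the change is at most −18.515 + 20.78 ≈ +2.3.

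**6. Consequence for all 57, at the cap of about +2.27.**

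| Quantity | From 8.5–8.6, at the cap | From 8.2–8.3 |
|---|---|---|
| Mean change, total scale | (56 × (−18.515) + 2.27)/57 = −18.15 | −17.91 |
| Per item | 18.15/9 = 2.017 | 1.99 |
| SD | √[(55 × 7.26² + (56/57) × 20.79²)/56] = 7.70 | 8.17 |
| \|t\| | 18.15/(7.70/√57) ≈ 17.8 | 16.542 |
| d | 17.8/√57 ≈ 2.36 | 2.19 |

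A lower change for that participant makes the mean more negative, and |t| stays at about 17.8 or more. At 0, for example, the mean is −18.20 and |t| is 18.1.

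**The case against.** The strongest reply is that the primary hypothesis was tested. SAP 7 plans effect sizes for an overall change, and 8.2–8.3 report an overall t and d that agree with each other at n = 57. With complete data, dividing a nine-item sum by nine leaves |t|, p and |d| unchanged. That stands. A reader might infer from SAP 7 that nine item tests replaced the single declared hypothesis, and the documents do not support this.

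Two other strong readings also fail:

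- *A 2-point worsening.* Taking +1.99 literally under the protocol's sign gives this. But 8.1 and 8.2 both speak of improvement, and the item differences use the same positive convention. The sign difference is one of convention, and the negative value in 8.6 is what the protocol's definition would give.
- *No precision at all.* An SE follows from 8.2: 1.99/16.542 = 0.120 per item, or a 95% interval of about 1.75 to 2.23. What is missing is a printed interval on the endpoint's own scale.

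It is also fair that 8.6 omits only one person in 57, and that all nine item p-values (below .001) would survive a Bonferroni threshold of 0.05/9 = 0.0056.

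None of this removes the conflict in the working. The argument that the overall t already tests the endpoint assumes that 1.99 is the total divided by nine, and on that assumption the SAP's other figures contradict it.

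**Conclusion.** The point holds, and the results section is wrong as written. The protocol's primary endpoint is not reported for all 57 in its declared units and sign, with an SD and 95% CI. The figures in 8.2–8.3 and 8.5–8.6 cannot all describe the same total-score change: −17.91 against −18.15 or lower, |t| 16.542 against about 17.8 or more, d 2.19 against about 2.36 or more.

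The gap in the mean is small, about a quarter of a point at its narrowest. Direction, statistical significance and the description of the effect as very large are not at risk. What is at risk is the accuracy of the headline difference, t, d and g.

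Assumptions:

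- 1.99 is a nine-item average. The SAP does not say so, but the item differences exclude a total.
- Every completed survey had all nine items answered.
- The improvement score ranked in 8.5 is the one summarised in 8.6, ranked from low to high. If the ranks ran the other way, the readmitted participant would be among the largest improvers and the mismatch would grow.

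A reader might be tempted to take −17.91 as the endpoint, or to build an interval from 8.6 by assuming a value for the readmitted participant. Neither is safe. The first conflicts with 8.5–8.6, and no document gives that participant's change. The documents also do not show which set of figures is in error.

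**What to change.** - In SAP 6.1 and 7, define the primary outcome as change in total EHFScB-9 (sum of nine items, 9–45), post minus pre, negative meaning better, in all 57 participants, with a paired t-test as its analysis. Label the nine item tests as secondary.
- In SAP 8.2–8.3, report the mean change, SD, 95% CI, paired t and effect size for all 57, recomputed from the raw data. Do not obtain them by multiplying 1.99 by −9. If a per-item average is kept, label it as such.
- Use one sign convention in 8.1, 8.2, 8.5 and 8.6.
- Reconcile 8.2–8.3 with 8.5–8.6, and say which figure was wrong and why (for example scoring, missing items or a different variable).

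The cost is a check of the raw data, one rerun of a paired analysis, and possibly a restated headline difference, t, d and g. No new data are needed.

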8.1 EHFSB-9 Pre/Post Ranges and Notable Item Improvements

Pre-intervention scores ranged from 1.65 to 4.00, indicating moderate to low engagement in heart failure self-care practices. Post-intervention scores improved substantially, ranging from 1.02 to 1.26. The most notable improvements were observed in recognizing weight gain (Q4), responding to fatigue (Q6), and daily weight monitoring (Q1), with mean differences of 2.86, 2.63, and 2.37, respectively.

8.2 Paired t-test Findings

Paired-samples t-tests confirmed statistically significant improvement in all nine self-care behaviors, with p -values $< .001$. The overall mean difference between pre- and post-intervention scores was 1.99, with a t -value of 16.542.

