8.3 Effect Sizes

Effect size calculations supported the clinical relevance of the intervention (Cohen’s $d = 2.19$; Hedges’ $g = 2.16$), representing a very large effect.

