8.5 Readmission Outcomes and Mann–Whitney U Test (Exploratory)

Of the 57 participants, 56 (98.2 percent) were not readmitted, and 1 participant (1.8 percent) experienced a heart failure-related readmission within 30 days. To assess whether readmission status influenced self-care improvement, a Mann–Whitney U test was conducted to compare EHFSB-9 improvement scores between readmitted and non-readmitted groups. Results indicated no statistically significant difference between groups (Mann–Whitney $U = 5.500$; Wilcoxon $W = 1601.500$; $Z = -1.370$; Asymptotic Sig. (2-tailed) = .171; Exact Sig. [2*(1-tailed Sig.)] = .211). Interpretation is limited by the extremely low number of readmissions ($n = 1$), which rendered the comparison underpowered.

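### The primary result in SAP 8.2 and 8.3 (mean difference 1.99, t = 16.542, d = 2.19, g = 2.16) cannot be reconciled with the total-score changes in SAP 8.5 and 8.6, which cover the same 57 participants.

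*SAP*

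**What the plan says.** Protocol 1.2 defines the primary outcome: "Primary Endpoint: Mean change in total EHFScB-9 score (post minus pre"). Protocol 8.1 fixes the scoring: "The total score is the sum of items (range 9–45"). SAP section 3 gives the analysis set: "Actual sample: N = 57 participants with complete pre- and post-intervention EHFScB-9 assessments".

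The SAP then reports results in two places.

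- **SAP 8.2 and 8.3, all participants.** "The overall mean difference between pre- and post-intervention scores was 1.99", "with a t -value of 16.542". The effect sizes are Cohen's d = 2.19 and Hedges' g = 2.16, introduced with the statement: "Effect size calculations supported the clinical relevance of the intervention". The scale of the 1.99 is not given.
- **SAP 8.5 and 8.6, by readmission status.** Of the 57, 56 were not readmitted and 1 was. For the 56, "the mean improvement score was -18.52 (SD = 7.26), with a median of -20.00 and a range of 30.00". The Mann–Whitney comparison gives U = 5.500 and "Wilcoxon $W = 1601.500".

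**The concern.** The two sets describe the same people, apart from the one readmitted participant who is left out of 8.6. A value of 1.99 cannot be a change in the 9–45 total when 56 of the 57 average -18.52, so it must be a per-item average. With all nine items answered, that average is the total change divided by 9. Dividing every score by 9 leaves t and d unchanged. The 57-person mean, SD, t and d should therefore follow from 8.6 plus one unknown number, the readmitted participant's change. If no possible value of that number links the two sets, at least one set is wrong or mislabelled.

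This is the primary result and the only effect size, and SAP 8.3 rests its claim of clinical relevance on it. Anyone extracting the SD of change for a meta-analysis or a later sample-size calculation would get a different answer from each section.

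**Working it through.** **Inputs.** n = 57 (SAP 3), split 56 and 1 (SAP 8.5). Nine items on a 5-point scale, total 9–45 (Protocol 8.1), so a change lies between -36 and +36. Mean difference 1.99 and t = 16.542 (SAP 8.2). d = 2.19 and g = 2.16 (SAP 8.3). For the 56: mean -18.52, SD 7.26, median -20, range 30 (SAP 8.6). U = 5.5 and W = 1601.5 (SAP 8.5). Let x be the readmitted participant's change in total score, post minus pre.

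**Step 1. Reproduce 8.2 and 8.3.**
- d = t/√n = 16.542/√57 = 2.191.
- g = d × (1 − 3/(4×56 − 1)) = 2.191 × (1 − 3/223) = 2.162.
- Both match, so this is a paired analysis of 57 and it agrees with itself.
- Implied SD of change: 1.99/2.191 = 0.908 per item, or 8.17 total points (8.15 to 8.19 with rounding of the 1.99).

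**Step 2. What the mean requires of x.**
- The only whole-number sum over 56 people that rounds to 18.52 is 1037 (1037/56 = 18.518).
- The sums over 57 people that round to 1.99 per item are 1019 to 1023 (divide by 57 × 9 = 513).
- So x = 1037 − 1023 = +14 up to 1037 − 1019 = +18, a marked worsening.

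**Step 3. What t requires of x.** Pooling the 56 with x gives
- mean = (−1037 + x)/57
- SD² = [55 × 7.26² + (56/57) × (x + 1037/56)²]/56
- t = |mean| × √57/SD.

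With the SD in 8.6 varied over its rounding interval (7.255 to 7.265), x = +11 gives t = 16.59 to 16.61 and x = +12 gives 16.44 to 16.46. No whole number from -36 to +36 gives 16.542. The values near it also miss on the mean, which rounds to 2.00 per item at x = +11 and +12. At the +14 to +18 that the mean requires, t is 15.6 to 16.2. So 8.2 and 8.6 conflict before 8.5 is used.

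**Step 4. What 8.5 and 8.6 allow for x.**
- W belongs to the 56: 56×57/2 + 5.5 = 1601.5. The readmitted participant's rank is 57×58/2 − 1601.5 = 51.5 of 57.
- The half rank means a tie, and at least 6 of the 56 had a change as high as x or higher.
- The minimum cannot exceed the median of -20, so with a range of 30 the maximum among the 56 is at most +10. Hence x ≤ +10.
- The one-sided Chebyshev bound with 6 of 56 at or above x gives x ≤ −18.518 + 7.265 × √(55/56) × √(50/6) = +2.3, so x is at most +2.
- A rank of 51.5 also places x above the median of the 56, so -20 is a safe lower limit.

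**Step 5. The 57-person result that 8.5 and 8.6 imply.**

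| | Mean change, total | Per item | SD, total | t | d |
|---|---|---|---|---|---|
| x = -20 | -18.54 | 2.06 | 7.20 | 19.45 | 2.58 |
| x = -10 | -18.37 | 2.04 | 7.28 | 19.04 | 2.52 |
| x = +2 | -18.16 | 2.02 | 7.69 | 17.82 | 2.36 |
| SAP 8.2 and 8.3 | -17.91 (1.99 × 9, sign as post minus pre) | 1.99 | 8.17 (implied) | 16.542 | 2.19 |

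The corresponding g is 2.33 to 2.54, against 2.16 printed. If the ranks had been taken in the opposite direction, x would lie between -36 and -20, where t is about 18.8 to 19.5, so that reading does not help.

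**The case against.** The strongest reply is that the SAP never says what the 1.99 is. SAP 6.1 defines the change score only for the between-group comparison, and no scoring rule is given for the overall figure. If 8.2 used another composite, or if blank items were summed in one analysis and averaged in the other, the same people could yield both sets. The fault would then be an undefined or mislabelled primary result, not an arithmetic slip. This is possible, but nothing in the documents supports it. SAP 3 reports complete assessments, and Protocol 8.1 defines the score as a plain sum. The improvement total implied by 8.5 and 8.6 is 1035 to 1057 points, against 1019 to 1023 for 1.99 per item. That gap of 12 to 38 points is more than a stray blank item would explain. The correction needed would also be the same.

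Three further points stand:
- The -18.52 (SD 7.26) belongs to 56 participants, not 57. The check allows for this by trying every value for the missing person.
- The 8.2 and 8.3 figures agree with one another, so the conflict is between sections and does not by itself show that 8.2 is the faulty one.
- The practical effect is modest. The mean differs by about 0.03 to 0.07 per item, the printed figures are the less favourable ones, and direction, significance and the very large effect remain under either set.

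**Conclusion.** The concern holds. SAP 8.2 and 8.3 on one side and SAP 8.5 and 8.6 on the other cannot both describe complete nine-item scores from the same 57 people. The mean requires the readmitted participant to have worsened by 14 to 18 points, t would need a value between +11 and +12, and the rank data allow at most +2. The printed t and d are about 7% to 15% below what 8.5 and 8.6 imply. The SD of change is 8.17 points by one route and 7.2 to 7.7 by the other.

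The conclusion about the mean assumes that 1.99 is the total change divided by 9 on complete data. The conclusion about t does not use the 1.99; it assumes only that t was computed on the total, or on the total divided by 9, for these 57. The documents do not show which set is wrong. The finding that scores improved is not in doubt. The size and spread of the primary estimate are.

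**What to change.** From the locked REDCap export, recompute each participant's pre total, post total and change (post minus pre) on the 9–45 scale. Run one paired t-test on the 57 totals, and report the mean change, SD, confidence interval, t, d and g with the scale and sign stated. Rerun the summaries and the rank test for 8.5 and 8.6 from the same file. Then correct 8.2 and 8.3, or 8.5 and 8.6, or both, so that every figure comes from one dataset, and state which figures were wrong and why. If the 1.99 proves to be a different composite or to involve missing items, define it, give the missing-item rule, and still report the protocol's total-score endpoint for all 57. The cost is under an hour of reanalysis plus corrected text, with no new data.
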